# 5.1.2 Electronic Data Capture

An electronic data capture (EDC) system will be utilized by study site personnel to transfer study data from source records (medical records and/or source document worksheets) onto common eCRFs. This system is a web-based, secure electronic software application (Medidata® Rave, Medidata® Rave, [name]). This system was designed and is developed and maintained by Medidata in a manner that is compliant with national and international GCP data protection/data privacy and electronic record/electronic signature (e.g., 21 CFR Part 11) regulatory requirements. The EDC system will be used to facilitate the collection of all study data at the site. Designated site personnel will be responsible for entering subject data into the EDC system. All external and Sponsor internal users will be trained on the EDC application at a level dependent on their planned function. An EDC digital User Manual will be available under the help menu within the Medidata® Rave website to assist in the collection and entry of source data into the electronic casebook.

There is a 24/7/365 Help Desk Support line staffed by the outsourced vendor that will be available to respond to questions.

# 5.1.3 Data Collection

Each EDC eCRF will be completed by the PI or PI's designee. Every effort should be made to respond to all monitoring and/or data management questions on each eCRF as completion of the data is required by the protocol. A unique ID number will identify each subject. The subject's unique ID number will be visible on each eCRF. At no time should the subject name appear on the eCRFs.

All data should be recorded accurately and completely. The Investigator is responsible for reviewing and approving each completed eCRF. Assurance of overall review and approval will be documented by the Investigator electronically signing each subject's electronic casebook.

# 5.1.4 Data Correction

Required data corrections to eCRFs will be prompted via automated electronic edit checks and/or queries manually created by Sponsor reviewers. The change(s), individual making the change(s), and time the change(s) were made to the eCRFs will be automatically captured in the audit trail within Medidata® Rave.

# 5.1.5 Data Privacy

The collection, use, and disclosure of all personal data, including subject health and medical information, are to be maintained in compliance with applicable personal data protection and security laws and regulations that govern protected health information and the informed consent given by each study subject. When collecting and processing such personal data, appropriate measures are to be taken to maintain the confidentiality of subject health and medical information and

to prevent access by unauthorized persons.

#### 5.1.6 Record Retention, Inspection, and Custody

The PI must maintain all documentation related to the study until they receive Sponsor notification. The PI will allow representatives of the Sponsor, the FDA, or other applicable government regulatory agencies to inspect all study records, eCRFs, and corresponding portions of the subject's office and/or hospital medical records at regular intervals during the study. These inspections are to verify adherence to the protocol, integrity of the data being captured on the eCRFs, and compliance with applicable regulations.

Subject medical records will be maintained in a confidential manner. Study reports will not identify subjects by name. These reports may be submitted to the FDA and/or applicable regulatory authorities.

If custody of the records is transferred, notice of such a transfer should be given to the Sponsor no later than 10 working days after the transfer occurs.

# 5.2 MEDICAL DICTIONARY CODING

Medical dictionary coding of verbatim AE, and SAE captured on eCRFs will be performed using a coding thesaurus algorithm. The Medical Dictionary for Regulatory Activities and World Health Organization Drug Dictionary will be used after data entry and query resolution, via auto-encoding and interactive coding processes.

# 6.0 DATA QUALITY ASSURANCE

Steps to be taken to assure the accuracy and reliability of data include the selection of qualified investigators and appropriate study centers, review of protocol procedures with the Investigator and associated personnel prior to the study, and periodic monitoring visits by the Sponsor. The Sponsor will review eCRFs for accuracy and completeness during on-site monitoring visits or periodic reviews of the EDC system; any discrepancies will be resolved with the Investigator or designees, as appropriate. The data entered into the clinical study database will be verified for accuracy.

# 6.1 INVESTIGATOR TRAINING

Prior to screening subjects for this study, the PI, sub-investigators, study coordinators, and other designated staff (as applicable) will be provided information on study execution, data collection, and procedures specific to this clinical protocol.

#### 6.2 MONITORING

This study will be monitored by the Sponsor to ensure:

- The rights and well-being of the subjects are protected;
- Reported study data is accurate, complete, and verifiable from source documents; and
- The conduct of the study is in compliance with the currently approved protocol/amendment(s), applicable GCPs, and with applicable local/regional regulatory requirements.

The extent and nature of monitoring will be predetermined and based on considerations

such as the objective, design, complexity, and endpoints of the study and mutually agreed to by the Sponsor and investigators. Monitors will comply with established written standard operating procedures as well as procedures (i.e., monitoring plan) specified by the Sponsor for monitoring this study. These monitoring procedures are characterized in the monitoring plan for this study.

# 6.3 PROTOCOL DEVIATIONS

A deviation (any activity conducted outside the parameters established by the study protocol) can be identified from a number of sources. Potential sources include, but are not limited to: a member of the Investigator's staff, a Sponsor representative during monitoring visits, or a member of the data management or statistical groups when entering or analyzing data. Regardless of the source, it is crucial to document the deviation. The PI will report protocol deviations to the IRB/EC as required by the IRB/EC procedures. All deviations will be captured in the source as well as the eCRF.

# 7.0 STATISTICAL METHODS PLANNED IN THE PROTOCOL AND DETERMINATION OF SAMPLE SIZE

# 7.1 STATISTICAL AND ANALYTICAL PLANS

The Sponsor's Data Management and Biostatistics groups will be responsible for the analysis of data from this protocol. A comprehensive and detailed Statistical Analysis Plan (SAP) will be finalized prior to database lock and will supplement the statistical design and analysis described in this section.

Categorical variables will be summarized descriptively by frequencies and associated percentages. Continuous variables will be summarized descriptively by number of subjects, mean, standard deviation, median, minimum, and maximum.

# 7.2 DETERMINATION OF SAMPLE SIZE

Approximately 250 subjects will be randomized in the study in a 1:1 ratio to standard of care or powered vascular stapler. Historical clinical study data on a similar powered surgical stapler demonstrated a need for staple line interventions in approximately 6% of firings on the pulmonary artery or pulmonary vein. This data also showed an average of 2.6 to 2.9 firings per subject, and it is expected, given differences in device design and procedure, that each subject will require 2 to 3 firings on the renal vein or renal artery in the current study with powered vascular stapler.

Given that it is expected to have a minimum of 300 firings in each group, the sample size of approximately 250 subjects is considered adequate for descriptive summarization of the primary performance endpoint, i.e. number and frequency of intra-operative surgical interventions. Assuming an approximate background intervention rate of 6%, the given sample size will provide reasonable precision in the estimation of the intervention rate to an expected margin of error for a 95% confidence interval of at most 2.9% for each group.

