Approximately 250 subjects were planned to be randomized in the study in a 1:1 ratio to SOC or PVS. Historical clinical study data on a similar powered surgical stapler demonstrated a need for staple line interventions in approximately 6% of firings on the pulmonary artery or pulmonary vein. This data also showed an average of 2.6 to 2.9 firings per subject, and it is expected, given differences in device design and procedure, that each subject would have required 2 to 3 firings on the renal vein or renal artery in the current study.

Given that it was expected to have a minimum of 300 firings in each group, the sample size of approximately 250 subjects total was considered adequate for descriptive summarization of the primary performance endpoint, i.e. number and frequency of intra-operative surgical interventions. Assuming an approximate background intervention rate of 6%, the given sample size was to have provided reasonable precision in the estimation of the intervention rate to an expected margin of error for a 95% confidence interval of at most 2.9% for each group.

During development of the protocol with the Notified Body (TUV) following their decision to grant CE mark to the device, a formal hypothesis was not defined for the study; however, to establish that the hemostasis intervention rate of PVS is not increased compared to SOC, an acceptance criterion was developed and a 95% confidence interval for the difference in the proportion of firings requiring interventions for PVS minus SOC will be calculated. The powered vascular stapler will be considered to have acceptable performance if the upper bound of the 95% confidence interval does not exceed 3%.

While the given sample sizes were expected to provide reasonable precision for estimation of the hemostasis intervention rate within each treatment group, the study was not sufficiently powered for demonstrating that the between treatment group comparison could achieve the 3% acceptance criterion. The given sample sizes are not large enough to control expected variability of the difference in rates between groups with a high probability, even if the true intervention rates are equivalent, thus increasing the likelihood of not meeting this acceptance criterion.

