10.4 Primary Endpoint Analyses

For the primary performance endpoint, summary statistics and 95% confidence intervals will be provided for the number and frequency of interventions by randomized treatment group. An intervention is defined as any firing which required a hemostasis intervention.

To account for the potential dependence among firings within a subject, the 95% confidence interval within each treatment group will be estimated using a bootstrap approach. For each subject, the outcome of each firing will be represented by a vector of 0's (indicating no intervention needed) and 1's (indicating an intervention was needed). This vector will be re-sampled with replacement to generate a bootstrap sampled vector of observations for each subject. Then, the proportion of observations requiring intervention for each subject will be calculated from this bootstrap vector. After obtaining a sample proportion of firings requiring intervention for each subject, the mean of these sample proportions will be calculated across all subjects within that treatment group to provide an estimated sample proportion of firings requiring intervention based on 1 iteration of the bootstrap process. This process will then be repeated a minimum of 5000 times to generate a sampling distribution for the proportion of firings requiring intervention within each treatment group. The mean of this sampling distribution will be provided as the point estimate of the

proportion of firings requiring intervention for that treatment group and the 95% confidence interval will be estimated by the lower 0.025 and upper 0.975 percentiles of this sampling distribution.

The table below demonstrates 1 iteration of this bootstrap process within a treatment group.

Subject ID	Observed Data Vector	Bootstrap Sampled Vector	Bootstrap-Based Sample Proportion
1	(0, 0, 1, 0, 0)	(0, 1, 0, 1, 0)	0.40
2	(0, 0, 0)	(0, 0, 0)	0.0
3	(0, 1, 0, 0)	(1, 0, 0, 0)	0.25
4	(0, 0, 1, 0, 0)	(0, 0, 0, 0, 0)	0.0
5	(0, 0)	(0, 0)	0.0
...
...
125	(1, 0, 0, 1, 0)	(0, 1, 0, 0, 0)	0.20
Summary			Average of above proportions to get 1 observation in the sampling distribution of the proportion of firings requiring intervention.

The above re-sampling process will then be repeated a minimum of 5000 times to estimate the sampling distribution for each treatment group.

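### 300 firings per group is a reasonable expected count but not a minimum (the plan's inputs give 250 to 375), so a 2.9% ceiling on the margin of error is not assured

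*Protocol*

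**What the plan says.** Protocol 7.2 sets the size and allocation: "Approximately 250 subjects will be randomized in the study in a 1:1 ratio to standard of care or powered vascular stapler". It reports experience with a similar powered stapler on pulmonary vessels, where about 6% of firings needed an intervention, and adds "This data also showed an average of 2.6 to 2.9 firings per subject". For the present trial it expects that "each subject will require 2 to 3 firings on the renal vein or renal artery in the current study with powered vascular stapler".

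The next paragraph of 7.2 draws the conclusion. It begins "Given that it is expected to have a minimum of 300 firings in each group", calls the sample size adequate for descriptive purposes, and gives the precision at a 6% rate. SAP section 8 repeats the count and the precision, an "expected margin of error for a 95% confidence interval of at most 2.9% for each group". The Synopsis (Statistical Methods) also gives 300 as a lower limit, with the same 2.9%, but without the firings-per-subject range.

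None of these places names the interval method behind 2.9%, allows for subjects lost after randomisation, or mentions correlation. SAP 10.4 introduces a bootstrap as the primary within-group interval: "To account for the potential dependence among firings within a subject". The exact interval that treats firings as independent is secondary there.

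**The concern.** Calling 300 a minimum and 2.9% a maximum makes both worst-case statements. The first can be checked against the paragraph before it, and 2 firings in each of 125 subjects is fewer than 300. The second depends on the first and on treating every firing as an independent observation, whereas the SAP's own primary analysis allows that firings in one subject may be related.

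This matters because within-group precision is the only quantitative support offered for 250 subjects. SAP section 8 accepts that the trial is not adequately powered for the 3% criterion on the difference, and rests on reasonable precision within each group instead. That remaining claim should be stated as the inputs allow.

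**Working it through.** **Inputs.** Randomised subjects: about 250, 1:1, so about 125 per group (Protocol 7.2). Firings per subject: 2 to 3 expected here, 2.6 to 2.9 historically (Protocol 7.2, SAP 8). Rate p = 0.06. Two-sided 95% interval within group; the exact Clopper-Pearson method is the one the SAP names for independent firings (SAP 10.4). No within-subject correlation is given in the documents.

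**1. The plan's own figure.** At n = 300 and p = 0.06 there are 18 events. The Clopper-Pearson interval is 3.59% to 9.32%, so the half-width is (9.32 − 3.59)/2, or 2.86% before rounding the limits. The plain Wald half-width is 1.96 × √(0.06 × 0.94/300) = 2.69%. The stated 2.9% is therefore reproduced by the exact interval at 300 independent firings.

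**2. The firing count.**
- Low end: 125 × 2 = 250
- Midpoint: 125 × 2.5 = 312.5
- High end: 125 × 3 = 375
- Historical average: 125 × 2.6 = 325 to 125 × 2.9 = 362.5
- Mean needed for 300: 300/125 = 2.4 per subject

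The low end is 50 firings (17%) below 300.

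**3. Losses.** The Full Analysis Set needs a performed procedure and intervention data (Protocol 7.3). Protocol 4.4 requires withdrawal in some intraoperative situations and does not replace subjects who withdraw after randomisation. At 2.5 firings per subject, 300 firings need 300/2.5 = 120 of the 125 subjects. With an assumed 5% loss (not in the documents), the mean needed rises to 300/(125 × 0.95) = 2.53.

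**4. The margin over the plan's range, firings independent, p = 0.06.**

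| Firings per group | Exact half-width | Wald half-width |
|---|---|---|
| 250 | 3.15% | 2.94% |
| 300 | 2.86% | 2.69% |
| 312 | 2.80% | 2.63% |
| 375 | 2.54% | 2.40% |

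An exact half-width of 2.9% or less needs about 293 firings.

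**5. Correlation, as an illustration only.** Take the design effect 1 + (m − 1) × ICC, with m firings per subject, and apply the exact interval to the effective number of firings. The ICC values are assumed.

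| Firings (m) | ICC 0.05 | ICC 0.1 | ICC 0.2 | ICC 0.3 |
|---|---|---|---|---|
| 250 (2) | 3.24% | 3.32% | 3.48% | 3.63% |
| 300 (2.4) | 2.97% | 3.07% | 3.26% | 3.45% |
| 375 (3) | 2.67% | 2.80% | 3.04% | 3.26% |

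Example: m = 2 and ICC 0.1 give a design effect of 1.1, an effective n of 250/1.1 = 227.3, and a half-width of 3.32%. At 300 firings, an ICC of about 0.02 already brings the exact half-width to 2.90%.

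**The case against.** The best defence is that 300 is a cautious expectation described with the wrong word. A group total of 250 would require every subject to have exactly 2 firings. The midpoint of the range gives 312 and the historical average 325 to 362, all above 300, and the sentence itself speaks of what is expected. This stands as a defence of 300 as an expected count. It does not make 300 a minimum, because 2 firings per subject lies inside the plan's own range and losses only lower the total.

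A reader might go further and infer that 2.9% is an arithmetic error. The documents do not support that. The figure follows from 6% and 300 independent firings by the exact method, and even at 250 the plain Wald half-width of 2.94% rounds to 2.9%. Since the sizing text does not name its method, the figure fails at the low end under the exact interval but not, after rounding, under Wald.

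A reader might also take the correlated figures, such as 3.63%, as the trial's real margin. They rest on assumed correlations. Nor are they the width that the SAP's primary bootstrap would report: it resamples firings within each subject and keeps the subjects fixed, so its width does not follow the design-effect formula. How well that bootstrap captures between-subject variation is a separate question.

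Finally, it can be said that SAP section 8 already discloses the weakness. Its disclosure concerns the between-group comparison with 3%. On within-group precision the same section repeats the 2.9% limit without qualification.

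**Conclusion.** The point holds as a misstatement of the planning figures. Under the plan's inputs the firing count is 250 to 375 per group, with 300 a defensible expectation, and the limit of 2.9% is not assured. With independent firings and a 6% rate, the exact half-width runs from about 2.5% to 3.2%, so the worst case exceeds the stated limit by 3.15 − 2.9 = 0.25 percentage points. Positive within-subject correlation would add to the true uncertainty by an amount the documents do not allow one to fix; an assumed 0.1 gives about 3.3% at 250 firings.

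These results rest on 125 analysed subjects per group, a 6% rate and the exact interval. Losses from the Full Analysis Set would move them slightly in the unfavourable direction.

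One might infer that the trial needs more subjects or that its error rates are affected. Neither follows: the sizing is descriptive, no power or type I error figure depends on 2.9%, and a margin near 3% serves much the same descriptive purpose.

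**What to change.** In SAP section 8, and in Protocol 7.2 and the Synopsis if the protocol is amended:

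- Replace the minimum of 300 firings (in the Synopsis, the equivalent lower limit) with: *expected 250 to 375 firings per group*. The basis, 125 subjects with 2 to 3 firings each before any loss from the Full Analysis Set, can be given in brackets.
- Replace the 2.9% upper limit with: *about 2.5% to 3.2% (exact 95% interval, 6% rate, firings assumed independent; wider if firings within a subject are positively correlated)*.
- If a figure for correlated firings is wanted, label it as an illustration with its assumed value, for example about 3.3% at 250 firings with an assumed correlation of 0.1. Do not present it as a planned property of the trial.

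The cost is a slightly less favourable precision statement. Enrolment, endpoints, analyses and the 3% criterion are unchanged.

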# 7.3 ANALYSIS SETS

•

There will be three analysis sets defined:

The Full Analysis Set (FAS) will consist of all randomized subjects who had the

procedure performed and provide data on number of surgical interventions;

- The Per Protocol (PP) Analysis Set will consist of all subjects in the FAS who had no major protocol violations;
- The Safety Set consists of all randomized subjects on whom the procedure is started.

The primary performance endpoint analysis will be performed on the Full Analysis Set and subjects will be classified according to their randomized treatment group. The primary endpoint analysis will also be performed on the PP set as a sensitivity analysis to the results on the FAS. The summary of additional endpoints will also be performed on the Full Analysis Set. Analysis of the primary safety endpoint and adverse event summaries will be performed on the Safety Set.

# 7.4 ANALYSIS OF EFFECTIVENESS

Summary statistics and 95% confidence intervals will be provided for the number and frequency of interventions for the set of SOC subjects and PVS subjects separately. This will be performed based on the total number of firings. An intervention is defined as any firing which is classified as hemostasis intervention. To establish that the intervention rate is not increased compared to SOC, a 95% confidence interval for the difference in proportion of firings requiring interventions for PVS minus SOC will be calculated and powered vascular stapler will be considered to have acceptable performance if the upper bound of the 95% confidence interval does not exceed 3%.

Additional endpoints will be summarized with descriptive statistics and 95% confidence intervals as appropriate for continuous or categorical measurements.

# 7.5 STATISTICAL/ANALYTICAL ISSUES

#### 7.5.1 Handling of Dropouts or Missing Data

All summaries will be performed only on subjects undergoing the surgical procedure and only observed data will be summarized. There will be no imputation of data for early terminated subjects or for missing data within the database.

#### 7.5.2 Interim Analyses and Data Monitoring

No interim analysis is planned for this study.

# 7.5.3 Multicenter Studies

No adjustment for center is planned in the statistical analysis. Center specific analyses may be conducted pending within-center sample size to understand the effect that surgeon techniques and site standard of care may have on the overall results.

# 7.5.4 Multiple Comparisons/Multiplicity

No adjustment for multiplicity is necessary since multiple hypotheses are not being tested.

# 7.6 ANALYSIS OF SAFETY

The number and percentage of subjects requiring hemostasis interventions postoperatively that are classified as related to SOC/PVS for RA/RV transection (e.g. need for blood product transfusion or additional surgical procedure) will be summarized for each

group as a primary safety endpoint.

Safety will be assessed through the incidence of AEs and serious adverse events (SAEs), which will be coded using the Medical Dictionary for Regulatory Activities (MedDRA). The incidence of AEs will be summarized at the MedDRA system organ class and preferred term level. Incidence of AEs will also be summarized by maximum severity. All reported adverse events will be listed.

